Any adverse event that meets any of these criteria will be documented and reported as a serious adverse event. Participants will be queried for side effects and AEs at the 1-week telephone visit and each clinic visit (week 6, week 12). In addition, information on serious adverse events may also be reported to study staff spontaneously by participants between study visits. In addition to local reporting requirements, all serious adverse events will be recorded by clinic staff and forwarded to the study physician within 72 hours of knowledge of the event. SAEs will be collected and reported from screening to the end of the study follow-up period for an individual participant. SAEs will be followed until resolution, stabilization, or until it is determined that study participation is not the cause. The Principal Investigator will be responsible for timely reporting to the NIH and the DSMB. The Principal Investigator will provide reports of serious adverse events for review by the DSMB at their meetings.

In addition, standard clinical safety alerts will be employed. When a measurement attains a defined alert level as described in the bullet points below, study staff will immediately notify the study physician for further evaluation.

- Systolic BP >180 or diastolic >110
- Heart rate <40 bpm
- Serum potassium ≥ 6.0 mEq/L or ≤ 3.0 mEq/L
- Serum sodium <130 mEq/L or >155 mEq/L
- Serum total bicarbonate <15 mEq/L or >40 mEq/L
- Serum calcium <8 or >11 mg/dL

- Plasma glucose <50 mg/dL or >350 mg/dL
- Serum creatinine doubling from last value
- CBC hemoglobin <7.0 gm/dL
- “Acute Distress” (includes chest pain or other signs or symptoms constituting an emergency)

5. Benefits

Potential Benefits: Participants may not receive any direct benefit from participating in the study. However, participants may have improved blood pressure, glucose, lipid levels, and may have improvement in other risk factors for cardiovascular disease. Participants will receive multiple blood pressure and weight measurements, blood analyses, and urine analyses. If vital signs or lab values are clinically abnormal, participants will be referred to their primary care physician, or if they do not have a primary care physician, one will be assigned through the Tulane University Community Health Center, which is a part of the core clinical facilities. At the end of the study, we will provide the participants’ primary care physician with a copy of all the blood pressure, weight, and laboratory results. Participants will also receive free parking for each intervention and study visit, and a small financial compensation for their time. Finally, participants will receive a free consultation with a registered Research Dietitian at the completion of their time in the study.

Importance of the Knowledge to be Gained: Information from this study may contribute to the establishment of dietary guidelines for potassium supplementation and may inform scientific knowledge on the intake-response relationship between potassium supplementation and blood pressure. Furthermore, information from this study may contribute to reducing the burden of cardiovascular disease in Louisiana and the general US population. The study has potential for large clinical and public health impacts.

6. Remuneration

Participants will receive payments in the form of gift cards to a common vendor (e.g., Amazon or Walmart): \$40 for the second baseline visit, \$20 and a small study-branded gift worth approximately \$10 for return of the ABPM and randomization, \$60 for the 6-week visit, \$40 for the first 12-week visit, and \$60 for the second 12-week visit for a total of \$230. Additionally, participants will receive a free consultation with a registered Research Dietitian at the completion of their time in the study. Throughout the recruitment and screening process, no potential participant will be coerced or pressured in any way to participate - participation is completely voluntary.

7. Academic or Extra Credit

NA

8. Costs

Participants will pay for travel as necessary to attend study visits.

9. Alternatives

Potential participants will be assured they do not have to participate in the research.

10. Consent process and documentation

The proposed study will be conducted following strict guidelines for the protection of the rights of human volunteers. Verbal informed consent will be obtained before any pre-screening activities, including blood pressure screening in community settings. The trial informed consent document will be signed by all participants at the first screening/baseline visit. The informed consent form will be developed in the first year of the study and approved by the IRB. The consent form will clearly state the purpose, eligibility criteria, and protocol of the study, the potential benefits and risks of participation, and the subject's right to refuse to participate or withdraw. Prior to signing the informed consent, research staff will review the details of the consent form orally with the participant, and answer any questions that the participant has concerning participation in the study. In the case of potential participants with low or no literacy, the informed consent form will be read to the participant in its entirety and any questions will be answered prior to the participant signing or marking the form. Specifically, the following must be accomplished during the informed consent process:

- The participant must be informed that participation in the study is **voluntary** and that refusal to participate will involve no penalty or loss of benefits.
- The participant must be informed of the **purpose** of the study and that it involves **research**.
- The participant must be informed of any **alternative procedures**, if applicable.
- The participant must be informed of any reasonably foreseeable **risks**.
- The participant must be informed of any **benefits** from the research.
- An outline of safeguards to protect participant **confidentiality** will be included, as well as an indication of the participant's right to withdraw without penalty. This should be balanced with a discussion of the effect that withdrawals will have on the study, and the responsibility a participant has, within limits, to continue in the study if he or she decides to enroll.
- The participant must be informed of his or her right to have **questions answered** at any time and **whom to contact** for answers or in the event of research-related injury.

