The **P**otassium Intake-response **T**rial to **C**ontrol **H**ypertension (**PITCH**) will test the intake-response relationship between potassium supplementation and BP, which may (1) inform clinical guidelines on the optimal level of potassium supplementation for BP lowering among adults with elevated BP and hypertension and dietary guidelines for population intake and (2) lay the foundation for further investigations, including mechanistic studies and outcome trials. A large meta-analysis of RCTs identified a dose-response relationship between BP lowering and risk of CVD, with a 5 mm Hg reduction in systolic BP reducing major CVD events by 10%.⁸ Modeling studies suggest that as little as a one mm Hg reduction in the mean systolic BP in the US population would reduce >20,000 coronary heart disease, stroke, and heart failure events annually.^{30,31}

Our long-term goal is to establish effective, scalable, and sustainable nonpharmacological

interventions, like potassium supplementation, for primary prevention of CVD. The specific goal of PITCH is to study the intake-response effect for 4 levels of potassium supplementation on 24-hour systolic BP among adults with untreated elevated BP or hypertension. We will test the following hypotheses:

Primary hypothesis: Compared with placebo (0 mmol/day potassium supplementation), there is a progressive, linear dose-response relationship between increasing doses of oral potassium supplementation (30, 60, and 90 mmol/day or 1173, 2346, 3519 mg/day) and decreasing levels of 24-hour systolic BP from baseline to 12-weeks of follow-up, and the largest BP lowering effect will be observed with a dose of 90 mmol/day (3519 mg/day).

Secondary hypotheses: Potassium supplementation improves levels of 24-hour diastolic BP, and office, daytime, and nighttime systolic and diastolic BP, and these improvements are greater with increasing potassium intake.

Exploratory hypotheses: We will examine the effects of potassium supplementation on other CVD risk factors, such as sodium excretion, and study the mediating effects of potassium-induced changes in CVD risk factors on BP. In addition, we will explore treatment effects by subgroups, including age, sex, race, baseline BP, central adiposity, and baseline sodium and potassium intake.

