Throughout the entire investigation, strict quality assurance (QA) and quality control (QC) measures will be used. This section describes some of the approaches.

Manual of Procedures: We will develop a study protocol and detailed manual of procedures (MOP) that identifies and details standard procedures for all elements of data collection in the trial. The MOP will be adapted from MOPs used successfully in previous RCTs conducted within the Office of Health Research

Training and Certification: Office of Health Research personnel will be trained based on established and effective methods. Training will focus on core trial elements, such as recruitment, retention, intervention, blinding, and data completeness and quality. Periodic re-training/certification sessions will be conducted to ensure all trial-related procedures are being applied in a standard manner across all participants. Throughout the trial, the investigators will monitor every aspect of study performance throughout the trial to make sure that the objectives are met, that study visits are timely and comprehensive, and that data are complete and of high quality. The accuracy of all laboratory measures, particularly crucial exposure, outcome, and intervention monitoring variables, will be carefully scrutinized.

3G. Statistical Design and Power

The trial is designed to detect a 1.5 mm Hg reduction in 24-hour systolic BP for each additional 30 mmol/day supplemental potassium compared with placebo, assuming 60 mmol/day achieves a 3 mm Hg reduction based on meta-analyses.^{25–29,34,35,49} We calculated our sample size assuming: 90% statistical power; a 2-sided significance level of 0.05; and a standard deviation of 7 mm Hg in 24-hour systolic BP change based on prior BP RCT experience in this population.^{50,51} The sample size calculation assumes analysis using a 4-group dose-response contrast test and the estimated sample size for each group based on these assumptions is 47. To allow for an 85% follow-up rate, we will recruit 56 trial participants in each group for a total of 224.

3H. Data Management

All study data will be double-entered. The study coordinator will conduct quality control checks on all study forms, study measures, and laboratory data. Data will be cleaned and logically checked and entered into a secure REDCap database.

3I. Statistical Analysis Plan

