Intention-to-treat analyses will be conducted such that the primary and secondary study outcomes will be evaluated among participants according to their randomization assignment at study entry.

Preliminary Data Analysis: Baseline participant characteristics will be summarized as the mean \pm standard deviation or median (interquartile range) for continuous variables and number (%) for categorical variables. Intervention groups will be compared on baseline characteristics to identify possible baseline imbalances.

Analyses of Main Effects: In the analysis of the primary and secondary outcomes, we will test the hypothesis that increasing doses of supplemental potassium result in monotonically greater reductions in levels of outcomes from baseline to 12 weeks follow-up in an intake-response

fashion. To test this hypothesis, we will use linear regression and the F-test of the hypothesis that there is a linear trend in mean net response in outcomes across the 4 randomized groups over 12 weeks. Rejection of the null hypothesis ($\mu_0 = \mu_{30} = \mu_{60} = \mu_{90}$) indicates that there is a significant intake-response relationship (i.e., $\mu_0 \leq \mu_{30} \leq \mu_{60} \leq \mu_{90}$ and $\mu_0 < \mu_{90}$) where the net effects will be calculated as mean changes in outcomes from baseline to 12 weeks follow-up in the potassium supplementation groups minus mean change in outcomes in the placebo group). The linear contrast will be tested using contrast coefficients of -3, -1, 1, 3. This approach is standard for dose-response RCTs.^{52–54} The optimal dose will be defined as that which shows the greatest net decrease in systolic BP over 12 weeks compared with placebo.

Based on a prior meta-analysis, the intake-response shape of potassium supplementation on systolic BP is uncertain.²⁸ The proposed trial is designed to evaluate a linear intake-response effect but will have sufficient power to characterize other possible relationships, including threshold effects, using contrast structures like modified linear, quadratic, exponential, and sigmoid.^{52–54}

In additional analyses, we will use linear mixed effects regression models incorporating follow-up outcome measures at both weeks 6 and 12, and will conduct pairwise comparisons between randomized groups in an exploratory analysis.

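### A significant linear contrast is read as showing the full dose ordering, which it cannot show, and the sign of the means in that ordering is never defined

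*Combined protocol and SAP*

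**What the plan says.** Section 3I (Analyses of Main Effects) sets the test for the primary and secondary outcomes: "The linear contrast will be tested using contrast coefficients of -3, -1, 1, 3". Rejecting equality of the four means "indicates that there is a significant intake-response relationship", and a parenthesis gives the content of that conclusion as μ0 ≤ μ30 ≤ μ60 ≤ μ90 and μ0 < μ90. The same parenthesis explains how effects are formed: "net effects will be calculated as mean changes in outcomes from baseline to 12 weeks follow-up in the potassium supplementation groups minus mean change", with placebo as the group subtracted. It does not define μ, or say whether a fall in BP counts as negative or positive.

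The primary hypothesis in the introduction has two parts: a progressive, linear relationship between dose and 24-hour systolic BP, and that "the largest BP lowering effect will be observed with a dose of 90 mmol/day". Section 3G sizes the trial for the contrast with "a 2-sided significance level of 0.05" and "90% statistical power".

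Further on, section 3I calls the shape of the relationship uncertain, lists other contrast shapes (modified linear, quadratic, exponential, sigmoid), and makes pairwise comparisons exploratory. It names as optimal the dose with the greatest net decrease in systolic BP. None of these steps is tied to the ordering conclusion.

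**The concern.** The sentence is the interpretive rule for the trial's only primary hypothesis, and it claims more than the test delivers. A single contrast compresses four means into one number. Many sets of means give the same number, including sets in which a higher dose does worse than a lower one. Moving from a non-zero contrast to the whole ordering requires monotonicity as a premise, and the plan does not state it.

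A second gap is that the ordering cannot be read without knowing what μ is. Under one common convention the printed inequalities describe BP rising with dose.

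The shape of the intake-response relationship is what the trial is meant to contribute to clinical and dietary guidelines. If the rule is applied literally, a significant trend can be written up as an established dose ordering when the data do not establish one.

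**Working it through.** **Inputs.** From section 3G: two-sided alpha 0.05; power 90%; effect "designed to detect a 1.5 mm Hg reduction in 24-hour systolic BP for each additional 30 mmol/day supplemental potassium compared with placebo"; "a standard deviation of 7 mm Hg in 24-hour systolic BP change"; 47 evaluable per group, 56 recruited. From section 3I: c = (-3, -1, 1, 3). Means below are written as follow-up minus baseline, relative to placebo, in the order 0, 30, 60, 90 mmol/day.

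**Reproducing the sample size.** The planned means are (0, -1.5, -3, -4.5).
- Σc² = 9 + 1 + 1 + 9 = 20.
- Σcμ = 1.5 - 3 - 13.5 = -15.
- Normal approximation: n = SD² × Σc² × (1.960 + 1.282)² / (Σcμ)² = 49 × 20 × 10.51 / 225 = 45.8, so 46.
- Noncentral t with 4(n - 1) degrees of freedom: power 0.898 at n = 46 and 0.9045 at n = 47, so 47.
- 47 / 0.85 = 55.3, so 56 per group and 224 in total.

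The plan's figures reproduce, and they belong to the two-sided one-degree-of-freedom contrast. The three-degree-of-freedom F-test would have power of only 0.786 at n = 47.

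**What rejection depends on.** The standard error of the contrast is 7 × √(20/47) = 4.566. For given n and SD, the rejection probability depends on the means only through Σcμ. The profiles below, other than the planned one, are illustrative and do not come from the documents.

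| True means | Σcμ | P(reject) | Ordered as hypothesised? |
|---|---|---|---|
| (0, -1.5, -3, -4.5), planned | -15 | 90.5% | yes |
| (0, -3, -6, -4) | 3 - 6 - 12 = -15 | 90.5% | no, 90 worse than 60 |
| (0, -3, -4.5, -3) | 3 - 4.5 - 9 = -10.5 | 63% | no |
| (0, -3, -4.5, -1.5) | 3 - 4.5 - 4.5 = -6 | 26% | no |
| (0, -4.5, -4.5, 0) | 4.5 - 4.5 + 0 = 0 | 5% | no |
| (0, +1.5, +3, +4.5) | -1.5 + 3 + 13.5 = +15 | 90.5% | no, BP rises with dose |

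**What significant trials look like.** I simulated 400,000 trials at n = 47 and SD 7 and kept the significant ones. Under the planned linear truth, about 62% have all four observed means in decreasing order. Under (0, -3, -6, -4), about 8% do. The printed rule would draw the same conclusion from all of them.

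**How well adjacent doses are separated.** The SE of a difference between two groups is 7 × √(2/47) = 1.444. A true step of 1.5 mm Hg is detected with about 18% power, and the 95% CI half-width is about 2.8 mm Hg. At this size the data will rarely settle the order of neighbouring doses.

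**Sign of μ.** If μ is the size of the reduction, the planned means are (0, 1.5, 3, 4.5), the contrast is +15 and the printed ordering is right. If μ is follow-up minus baseline, the contrast is -15 and the hypothesised order is μ0 ≥ μ30 ≥ μ60 ≥ μ90, the reverse of what is printed.

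**The case against.** The contrast is a standard choice for a dose-response trial, and its p-value, type I error, power and sample size are all sound. That stands in full; the issue is only what is concluded from it.

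Several stronger readings are tempting, and the documents do not support them.
- **The ordering is printed backwards.** The sentence defines net effects, not μ, and the paragraph's hypothesis is about greater reductions. On a reduction scale the inequalities are correct. What is missing is the sign convention.
- **The contrast rejects equally often for any non-linear shape.** Equality holds only for profiles with the same Σcμ. The (0, -3, -6, -4) profile also needs a 6 mm Hg effect, above the planned maximum of 4.5. With effects no larger than 4.5, the non-monotone profiles in the table run from 63% down to 5%.
- **An effect at the top dose only breaks the rule.** A profile such as (0, 0, 0, -5) satisfies the weak ordering on the reduction scale, because flat segments are allowed. It conflicts only with a progressive, linear description.
- **Harm would be reported as success.** The hypothesis is directional, and reading direction from the estimate after a two-sided test is ordinary practice. On the reduction scale, μ0 < μ90 itself excludes harm. The point is only that the rule does not attach the sign to rejection.
- **The plan would report a monotone result against its own means.** Dose-specific net effects, other contrast shapes and pairwise comparisons are all planned, and the optimal-dose rule could pick a dose other than the highest. These analyses would expose a reversal. They are not linked to the ordering sentence, however, and section 3I treats all non-primary analyses as hypothesis generating.

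**Conclusion.** The stated inference is wrong as written and should be corrected. Rejection shows a non-zero linear trend component across assigned dose. It does not show the four-group ordering, and it does not test whether the effect is largest at 90 mmol/day.

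The size depends on the true shape, which the plan itself calls uncertain: at n = 47 and SD 7, the illustrative non-monotone profiles are declared significant with probability from 5% to 90.5%. Even if the planned linear effect is exactly true, roughly four in ten significant trials (100% - 62% = 38%) will not show ordered observed means. These figures assume normal outcomes, a common SD of 7 and 47 evaluable per group.

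The missing definition of μ is a clarity defect, not a demonstrated reversal. Nothing here affects alpha, the p-value, power or the 47/56/224 sample size, so this is a should-fix matter of interpretation and not a flaw in the test.

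**What to change.** Rewrite the decision paragraph in section 3I before unblinding:

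1. Define μ and its sign (follow-up minus baseline, or size of reduction) and write the ordering to match.
2. State the primary null as linear contrast equal to zero.
3. Limit the conclusion from rejection to a linear trend in the outcome across assigned dose, claimed as benefit only when the estimate is in the BP-lowering direction.
4. Describe the shape from the dose-specific net effects and pairwise differences already planned, with 95% CIs. Include the 90-versus-60 difference as the evidence on whether the effect is largest at 90 mmol/day.
5. Do not present monotonicity as established by the contrast. If it is to be assumed, say so.

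The cost is one reworded paragraph and a reporting commitment for estimates the plan already calls for. No participants, visits or alpha are needed. The only loss is a slightly narrower permitted conclusion, and the CIs for neighbouring doses will often be too wide to settle their order, which the report should say.

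### The optimal dose is defined as the arm with the largest observed fall in systolic BP, with no outcome named, no trend result required and no account taken of precision

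*Combined protocol and SAP*

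**What the plan says.** Section 3I (Analyses of Main Effects) sets out a linear trend test across the four arms for the primary and secondary outcomes. The paragraph then closes with the dose rule: "The optimal dose will be defined as that which shows the greatest net decrease in systolic BP over 12 weeks compared with placebo". Nothing else in the documents qualifies the rule.

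The opening statement of aims gives the result a purpose, saying that the trial may "inform clinical guidelines on the optimal level of potassium supplementation for BP lowering".

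The next paragraphs of 3I acknowledge that the shape of the response is not known, list alternative contrasts (including for a threshold), and provide exploratory pairwise comparisons between arms. None of these is connected to the choice of dose.

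**The concern.** The rule ranks three estimated means and names the largest. It returns a dose however close the three are. Where two or more doses work equally well, sampling error decides which is named. The estimate quoted for that dose then tends to be too large, because it was picked for being the largest.

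Two further gaps affect how the sentence is applied. Systolic BP is measured as 24-hour, office, daytime and nighttime values, and 3I covers primary and secondary outcomes together, so different measures could name different doses. The sentence also does not say whether a dose is named when the trend test is not significant.

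At stake is the statement most likely to be carried into guidance. A reader would take a named optimal dose as a finding that it beats the others.

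**Working it through.** **Inputs.** All are from section 3G, except the contrast, which is in 3I.
- Effect: "The trial is designed to detect a 1.5 mm Hg reduction in 24-hour systolic BP for each additional 30 mmol/day supplemental potassium compared with placebo", so the true net effects are 0, −1.5, −3.0 and −4.5 mm Hg.
- Error rates: "90% statistical power; a 2-sided significance level of 0.05".
- Variability: "a standard deviation of 7 mm Hg in 24-hour systolic BP change".
- Size: "the estimated sample size for each group based on these assumptions is 47". Section 3G raises this to 56 per arm (224 overall) for 85% follow-up.
- Contrast: "The linear contrast will be tested using contrast coefficients of -3, -1, 1, 3".

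**1. The plan's own figure.** n per arm = Σc² × [SD × (z₀.₉₇₅ + z₀.₉₀)]² / (Σcμ)².
- Σc² = 9 + 1 + 1 + 9 = 20.
- Σcμ = 1.5 − 3.0 − 13.5 = −15.
- n = 20 × (7 × 3.2415)² / 225 = 45.8, so 46 by the normal approximation.
- With the noncentral t, power is 89.8% at 46 and 90.5% at 47, so 47.
- 47 / 0.85 = 55.3, so 56 per arm and 224 in total. The stated sizes reproduce.

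**2. Precision between doses.**
- SE of one arm mean = 7/√47 = 1.02 mm Hg.
- SE of a difference = 7 × √(2/47) = 1.44 mm Hg; 95% half-width = 1.96 × 1.44 = 2.8.
- For adjacent doses 1.5 mm Hg apart, 1.5/1.44 = 1.04 standard errors, which gives about 18% power.
- 80% power would need 2 × [7 × (1.960 + 0.842)/1.5]² = 342 per arm.

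**3. Behaviour of the rule.** Arm means were simulated as normal with SE 1.02, at least 1,000,000 trials per scenario. The active arm with the largest observed fall was named. Overstatement is the mean amount by which its observed net effect exceeds its true one. The two plateau rows are assumed shapes, because the documents give no plateau values.

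| True net effect at 30 / 60 / 90 (mm Hg) | Named 30 / 60 / 90, rule as written | Overstatement (mm Hg) | Named 30 / 60 / 90, after a significant beneficial trend | Overstatement (mm Hg) |
|---|---|---|---|---|
| −1.5 / −3 / −4.5 (planned line) | 1 / 15 / 84% | 0.37 | 0.5 / 13 / 86% | 0.56 |
| −3 / −3 / −3 (plateau from 30) | 33 / 33 / 33% | 0.86 | 17 / 33 / 49% | 1.6 |
| −1.5 / −3 / −3 (plateau from 60) | 6 / 47 / 47% | 0.69 | 2 / 42 / 57% | 1.3 |
| 0 / 0 / 0 (no effect) | 33 / 33 / 33% | 0.86 | 2 / 21 / 77% | 3.4 |

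In the no-effect row the gate is passed in only 2.5% of trials. On the two plateaus it is passed in about 50% and 63%.

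**4. Check by formula.** With three equal active arms, the expected overstatement is the mean of the largest of three standard normals times the SE: 0.846 × 1.02 = 0.86 mm Hg, which is 29% of a true 3.0.

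**5. Sensitivity (plateau from 30, ungated).** With all 56 per arm analysed, overstatement is 0.79. With an assumed SD from 6 to 9 and 47 per arm, it runs from 0.74 to 1.11.

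**6. Why gating raises the bias.** The contrast puts most weight on the placebo and 90 mmol/day arms. Trials that pass tend to have a chance low in the 90 arm, a chance high in placebo, or both. The first favours naming 90; the second inflates every net effect.

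**The case against.** The strongest reply is that the rule works reasonably well under the only response the plan quantifies. On the planned line it names 90 mmol/day in 84% of trials, and when it does so the mean overstatement is 0.21 mm Hg, about 5% of 4.5. That stands. The larger figures need a plateau, which is assumed here. A reader might infer that the plan expects a plateau; it says only that the shape is uncertain and that threshold effects are among those it could characterise.

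A reader might also infer that the trial will name a dose even if nothing works. The text permits this but does not clearly intend it. The sentence follows the discussion of what rejecting the null shows, so test first and then name the dose is a natural reading. On that reading a dose is named in about 2.5% of trials under no effect, and the choice on a plateau tilts upward instead of being an even draw. The gate is not written down, however, and it makes the overstatement worse.

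A third inference, that the trial ignores harms, is not supported. Symptoms and serum potassium are collected and reviewed, with DSMB oversight (3C, 3D, 4A, 4B), and the aims speak of the optimal level for BP lowering. Only the dose-naming sentence leaves harms out.

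Finally, the primary outcome is identified as 24-hour systolic BP throughout, so its absence from this sentence is a drafting gap. The pairwise comparisons and alternative contrasts would give readers more than one named dose, but they do not govern which dose is called optimal.

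**Conclusion.** The point holds as a defect in the dose-naming rule. As written, the rule cannot tell a better dose from a luckier one, because a between-dose difference has a standard error about as large as a planned dose step. On a plateau, the choice among equally effective doses is chance and the effect is overstated by roughly 0.7 to 0.9 mm Hg ungated, or 1.3 to 1.6 if a significant trend is required. On the planned line the overstatement is 0.37 ungated and 0.56 gated.

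These figures rest on SD 7, 47 analysed per arm, normal arm means and, for the plateau rows, the assumed shapes. The trend test, its alpha and N = 224 are not in question. Nothing here bears on which dose is right.

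**What to change.** Reword the sentence in 3I, before unblinding, so that:

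1. It refers to 24-hour systolic BP, change from baseline to 12 weeks.
2. A dose is named only if the primary trend test is significant in the beneficial direction.
3. The named dose is described as the one with the largest observed decrease. It is reported with all three net effects and all between-dose differences, each with a 95% CI, and with the bootstrap probability that each dose has the largest effect. The bootstrap should use arm means: a fitted straight line can only ever rank an end dose (30 or 90) first among the active arms.
4. Where the intervals do not separate the doses, the report says so and claims no single optimal dose.
5. The chosen arm's raw estimate is flagged as subject to selection and shown beside the estimate from a dose-response model named in advance. The choice of model matters. On the plateau from 30, Σcμ = 3 − 3 − 9 = −9, so a straight line has slope −9/20 = −0.45 per contrast unit. With two units per dose step, it puts the net effect at 30 mmol/day at −0.9 when the truth is −3.
6. Serum potassium and symptom data, already collected, are tabulated by dose beside the BP effects, without prescribing how they should decide the dose.

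The cost is SAP wording, one bootstrap and the choice of a model; recruitment, visits and treatment do not change. The downside should be stated in the plan. Even under the planned line, the interval for 90 versus 60 mmol/day would exclude zero in favour of 90 in only about 18% of trials (17.7% with the t distribution), so adjacent doses not being separated is the expected outcome.
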